7.3 Healthcare Utilization Questionnaires

The Healthcare Utilization Questionnaires include the Hospitalization Questionnaire and the Positive Pressure Ventilation (PPV) and Intubation Questionnaire. The Hospitalization Questionnaire should be collected at hospital discharge or at final study visit/contact. The need for non-invasive or invasive ventilatory support within 24 hours prior to IP initiation and following IP initiation and within 48 hours following IP discontinuation should be collected as close as possible to the event.

8 ADVERSE AND SERIOUS ADVERSE EVENTS ASSESSMENT

8.1 Definition of Adverse Events, Period of Observation, Recording of Adverse Events

An AE is any untoward medical occurrence in a clinical investigation participant who has been administered a pharmaceutical product; it does not necessarily have a causal relationship with this treatment. An AE can therefore be any unfavorable and unintended sign (including an abnormal laboratory finding), symptom, or disease temporally associated with the use of an IP product, whether or not related to the IP.⁴⁰

As this study allows for pre-consenting of participants, all AEs will be collected from the time of IP initiation until the final study follow-up visit/contact stated in [Section 7.1](#). Where possible, a diagnosis rather than a list of symptoms should be recorded. If a diagnosis has not been made, then each symptom should be listed individually. All AEs should be recorded on the AE eCRF page and in source documents. In addition to untoward AEs, unexpected benefits outside the IP indication should also be recorded on the AE eCRF page.

All AEs must be followed for the durations described below. For AEs followed to closure, this indicates that an outcome is reached, stabilization is achieved (the investigator does not expect any further improvement or worsening of the event), or the event is otherwise explained. When appropriate, medical tests and examinations are performed so that resolution of event(s) can be documented.

For participants who terminate early from the study, prior to discontinuation as much information as possible as is available should be recorded for AEs/SAEs and their associated concomitant medication, especially those that may have led to the early termination.

8.1.1 Severity Categorization

The severity of AEs must be recorded during the course of the event, including the start and stop dates for each change in severity. An event that changes in severity should be recorded as a new event. Worsening of pretreatment events, after initiation of the IP, must be recorded as new AEs on the appropriate eCRF page.

The medical assessment of severity is determined by using the following definitions:

Mild: A type of AE that is usually transient and may require only minimal treatment or therapeutic intervention. The event does not generally interfere with usual activities of daily living.

Moderate: A type of AE that is usually alleviated with specific therapeutic intervention. The event interferes with usual activities of daily living, causing discomfort, but poses no significant or permanent risk of harm to the research participant.

Severe: A type of AE that interrupts usual activities of daily living, that significantly affects clinical status, or that may require intensive therapeutic intervention.

8.1.2 Relationship Categorization

A physician/investigator must make the assessment of the relationship between the IP and each AE. The investigator should decide whether, in their medical judgment, there is a reasonable possibility that the event may have been caused by the IP. If there is no valid reason for suggesting a relationship, the AE should be classified as “not related.” Otherwise, if there is any valid reason, even if undetermined or untested, for suspecting a possible cause and effect relationship between the IP and the occurrence of the AE, the AE should be considered “related.” The causality assessment must be documented in the source document.

The following additional guidance may be helpful:

Term	Relationship definition
Related	The temporal relationship between the event and the administration of the investigational product is compelling and/or follows a known or suspected response pattern to that product, and the event cannot be explained by the participant’s medical condition, other therapies, or accident.
Not related	The event can be readily explained by other factors, such as the participant’s underlying medical condition, concomitant therapy, or accident, and no plausible temporal or biologic relationship exists between the investigational product and the event.

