8.2.7 Regulatory Agency, Institutional Review Board, Ethics Committee, and Site Reporting

The Sponsor or its delegate is responsible for notifying the relevant regulatory authorities in the US of related, unexpected SAEs. For ex-US countries, the Sponsor will comply with local laws and requirements with regard to SAE reporting.

In addition, the Sponsor or its delegate is responsible for notifying active sites and central IRBs of all related, unexpected SAEs occurring during all interventional studies across the ganaxolone program.

The investigator is responsible for notifying the local IRBs, local EC, or the relevant local regulatory authority of all SAEs that occur at their site as required.

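### The guidance table in Protocol 8.1.2 is stricter than the prose above it and leaves events with both a plausible IP link and another possible cause in neither row

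*Protocol*

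**What the plan says.** Protocol 8.1.2 makes a physician or investigator judge each event as *related* or *not related*; there is no third category.

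- **Prose.** The question is whether "there is a reasonable possibility that the event may have been caused by the IP". If there is no valid reason to suggest a relationship, the event is not related. Otherwise it is related "if there is any valid reason, even if undetermined or untested, for suspecting a possible cause and effect relationship between the IP" and the event.
- **Table, Related row.** The timing "is compelling and/or follows a known or suspected response pattern to that product, and the event cannot be explained by" underlying illness, concurrent treatment or an accident.
- **Table, Not related row.** Two joined conditions: "The event can be readily explained by other factors", and "no plausible temporal or biologic relationship exists between the investigational product and the event".

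The table is introduced as extra guidance that may help. No sentence says which standard prevails if they differ.

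The label is used elsewhere. Protocol 8.2.7 makes the sponsor responsible for "notifying the relevant regulatory authorities in the US of related, unexpected SAEs", with the same limit for active sites and central IRBs. Protocol 8.2.4 requires reports of SAEs discovered after the study has completed only if they are considered related. Protocol 10.5 and SAP 3.3.1 tabulate related events, and the SAP also tabulates serious drug-related ones.

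**The concern.** Under the prose, another possible cause does not stop an event from being related. Under the table's Related row, it does. This matters here because confounding is built into eligibility: every participant has status epilepticus and has already received at least two antiseizure agents (Protocol 4.1).

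The protocol itself names overlapping causes. Hypotension was reported in 4 of 17 patients on IV ganaxolone in phase 2 (Protocol 2.1), and the synopsis rationale names it as a benzodiazepine effect. Cardiac arrhythmia is a reason to interrupt or stop IP (Protocol 6.2.4) and a complication of convulsive status epilepticus (Protocol 1.1).

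An investigator working from the table finds no row for such an event but must still tick one of two boxes. The alternative cause is the more visible fact, so *not related* is the natural choice. Two sites could then label the same event differently. The safety sections (8.1.2 and 8.2.2 to 8.2.7) describe only the investigator's causality assessment; they neither describe nor exclude a separate sponsor assessment.

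**Working it through.** Section 8.1.2 states no figure to reproduce. The check applies both rules to every combination of two factors.

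**Inputs (all from Protocol 8.1.2)**

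- Link to IP, three levels: none plausible; plausible but neither compelling in timing nor a known or suspected pattern; compelling or a known or suspected pattern.
- Alternative cause, three levels: cannot explain the event; could explain it, but not readily; readily explains it.
- Combinations: 3 × 3 = 9.

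**Rules**

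- Prose: related if the link is at least plausible; otherwise not related. This takes a plausible link as a valid reason to suspect the IP.
- Table, related: link compelling or known/suspected AND the alternative cannot explain the event.
- Table, not related: alternative readily explains AND no plausible link.

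| Link to IP | Alternative cause | Prose | Table |
|---|---|---|---|
| None plausible | Cannot explain | Not related | Neither |
| None plausible | Could explain | Not related | Neither |
| None plausible | Readily explains | Not related | Not related |
| Plausible | Cannot explain | Related | Neither |
| Plausible | Could explain | Related | Neither |
| Plausible | Readily explains | Related | Neither |
| Compelling or known | Cannot explain | Related | Related |
| Compelling or known | Could explain | Related | Neither |
| Compelling or known | Readily explains | Related | Neither |

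**Results**

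- Prose: 6 related + 3 not related = 9. Every combination is placed.
- Table: 1 related + 1 not related + 7 neither = 9.
- Of the 6 that the prose calls related, the table confirms 1 and leaves 6 − 1 = 5 unplaced. Four of the five have a possible alternative cause. The fifth has none, and fails only because its link is neither compelling nor a known or suspected pattern.
- No combination is related under one rule and not related under the other.

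These are counts of logical cases, not event frequencies.

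**Worked example.** Take early hypotension in a participant recently given a benzodiazepine. Phase 2 hypotension was 4/17 = 23.5%, so a suspected IP pattern exists; the benzodiazepine could also explain the event. The prose gives related. The table gives neither: Related fails on the alternative cause, and Not related fails on the plausible link.

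**What depends on the label**

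| Step | Depends on *related*? |
|---|---|
| In-study SAE to safety vendor within 24 hours (8.2.2, 8.2.4) | No |
| Investigator to local IRB, ethics committee or authority (8.2.7) | No |
| Sponsor to US authorities, active sites, central IRBs (8.2.7) | Yes, and must also be unexpected |
| SAE discovered after study completion (8.2.4) | Yes |
| All-TEAE and serious-TEAE tables (SAP 3.3.1) | No |
| Related and serious drug-related TEAE tables (Protocol 10.5, SAP 3.3.1) | Yes |

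**The case against.** The strongest reply is that the prose already decides every case, and decides confounded cases towards *related*; the table is only offered as help. An investigator reaches *not related* for a confounded event only by ignoring both the prose and the second condition of the table's own Not related row. This stands in part: a careful reader of the whole section gets the right answer. But a definition row that withholds the label from events the rule above it calls related is not harmless because it is optional, and nothing tells the reader to prefer the prose.

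The reply also correctly limits the consequences. In-study SAEs reach the vendor whatever the label, the DMC has ongoing access to safety data (Protocol 9.3), and all treatment-emergent events are tabulated by arm. The IP-stopping and withdrawal provisions that mention relatedness are discretionary, and neighbouring provisions need no relatedness judgement. Sponsor notification also requires the event to be unexpected, which rests on an Investigator's Brochure not available here. The phase 2 hypotension and somnolence rates (4/17 = 23.5% and 5/17 = 29.4%) are all-event rates, so they do not show a missed report. Assessors are blinded, so inconsistent labelling is not shown to favour either arm.

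A reader might infer more: that the two tests are opposites, that most intensive-care events fall in the gap, or that related SAEs go unreported altogether. The documents support none of these. The enumeration finds no direct reversal, no passage gives a distribution of events, and first-line in-study reporting is independent of the label.

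**Conclusion.** The point holds as a conflict of threshold and coverage within one section. The exposure is confined to three places: sponsor notification of related, unexpected SAEs; SAEs discovered after study completion; and the related-event summaries. No efficacy result is affected.

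The number of events affected cannot be estimated from the documents. The conclusion rests on two assumptions: that an event another cause could explain fails the table's condition "and the event cannot be explained by" such a cause, and that some investigators work from the table and resolve an unplaced event towards *not related*. The first follows from the wording; the second is plausible but undocumented. If every investigator follows the prose, nothing is lost. The correction is still worth making because it is specific and cheap, and it removes a definition that contradicts its governing rule.

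**What to change.** 1. Rewrite the two rows to match the prose. *Related*: a reasonable possibility that the IP caused or contributed to the event, even if other causes are possible. *Not related*: no reasonable possibility. This removes the requirement for compelling timing and the condition that nothing else can explain the event, and places every event in exactly one category.
2. State in 8.1.2 that the prose governs, and send the wording to sites.
3. Randomization stopped at 100 (Protocol 3.1.1; SAP 3.5), so new wording alone will reach few further assessments. Re-query, while still blinded and before final database lock, SAEs classed as not related solely because another cause existed.

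The cost is two table rows, one sentence, a site memo and a bounded set of queries, which is most of the work. The related-event table may look slightly less favourable, and some extra safety reports may follow.

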8.1.3 Outcome Categorization

The outcome of AEs must be recorded during the study in the eCRF. Outcomes are as follows:

- Fatal
- Not recovered/not resolved
- Recovered/resolved
- Recovered/resolved with sequelae
- Recovering/resolving
- Unknown

8.1.4 Symptoms of the Disease Under Study

Symptoms of the disease under study should not be classified as AEs as long as they are within the normal day to day fluctuation or expected progression of the disease and are part of the efficacy data to be collected in the study; however, significant worsening of the symptoms should be recorded as an AE. Specifically, SE signs and symptoms that were present at study entry and that varied in intensity over the duration of study treatment are not considered AEs unless in the investigator’s opinion there is an *unexpected* worsening of the events. However, if all seizure activity resolved and the participant returned to baseline status, but SE recurred, the event would then be recorded as an SAE.

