7.1.3 Follow-up Period (starting at IP discontinuation through Week 4)

Participants will have the follow-up period assessments/procedures collected following IP discontinuation (with or without taper) as noted in [Section 3](#). Assessments/procedures will be collected every 24 hours through 120 hours (or until hospital discharge) and at the time of hospital discharge, followed by weekly follow-up visits/contacts at Week 1, 2, 3 and 4.

Participants who discontinue IP without a taper, e.g., were administered IP for less than 2 hours, progress to anesthesia for seizure suppression or discontinue IP due to safety or any other reason, except due to withdrawal of consent, will have the follow-up assessments/procedures collected every 24 hours through 120 hours (or until hospital discharge) and at the time of hospital discharge, followed by weekly follow-up visits/contacts at Week 1, 2, 3 and 4.

The follow-up period for this protocol is approximately 4 weeks. Week 1, 2, 3, and 4 visits may be conducted as an inpatient visit, if the participant is still in the hospital, or as a telephone contact, if the participant has been discharged. Attempts should be made to have discharged participants return for one of these visits to be in person. The participant/participant's parent/guardian/LAR, as appropriate, will receive a follow-up contact weekly approximately 7 ± 3 , 14 ± 3 , 21 ± 3 , and 28 ± 3 days following the IP discontinuation date. If the hospital discharge visit corresponds to the Week 1, 2, 3, or 4 (± 3 days) visits, it can take the place of the weekly visit.

During these follow-up period visits/contacts, the site will follow-up on all SAEs and non-serious AEs, AE resolution that occurs, and concomitant medications. Adverse events and SAEs that are not resolved at the time of contact will be followed to closure (see [Section 8.1](#)). [Table 1](#) lists the assessments that should be collected during the follow-up visits/contacts.

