8.2.3 Serious Adverse Event Definition

An SAE is any untoward medical occurrence (whether considered to be related to IP or not) that at any dose:

- Results in death
- Is life-threatening. Note: The term “life-threatening” in the definition of “serious” refers to an event in which the participant was at risk of death at the time of the event; it does not refer to an event that hypothetically might have caused death if it were more severe.
- Requires inpatient hospitalization or prolongation of existing hospitalization. Note: Hospitalizations, which are the result of elective or previously scheduled surgery for preexisting conditions that have not worsened after initiation of treatment, should not be classified as SAEs. For example, an admission for a previously scheduled ventral hernia repair would not be classified as an SAE; however, a complication resulting from a hospitalization for an elective or previously scheduled surgery that meets serious criteria must be reported as an SAE.
- Results in persistent or significant disability or incapacity
- Is a congenital abnormality or birth defect
- Is an important medical event. Note: Important medical events that may not result in death, be life threatening, or require hospitalization may be considered an SAE when, based on appropriate medical judgment, they jeopardize the patient and may require medical or surgical intervention to prevent one of the outcomes listed in this definition. Examples of such medical events include allergic bronchospasm requiring intensive treatment in an emergency room or at home; blood dyscrasias that do not result in inpatient hospitalization, or the development of drug dependency or drug abuse.

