8.2.4 Serious Adverse Event Collection Time Frame

As this study allows for pre-consenting of participants, all SAEs (regardless of relationship to study) are collected from the time of IP initiation until the final study follow-up visit/contact stated in [Section 7.1](#) and must be reported to the Marinus Drug Safety vendor within 24 hours of the first awareness of the event.

In addition, any SAE considered “related” to the IP and discovered by the investigator at any interval after the study has completed must be reported to the Marinus Drug Safety vendor within 24 hours of the first awareness of the event.

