13 APPENDICES

APPENDIX 1 STATUS EPILEPTICUS CESSATION GUIDE

Status epilepticus cessation will be based on investigator judgment, guided by the following clinical and electrographic features:

1. The first 30-minute SE free period after IP initiation denotes the onset of SE cessation
2. Electrographically SE cessation should coincide with the beginning of the first 30-minute epoch of EEG which demonstrates seizure burden <20% and at least 50% less than during the 30 minutes prior to IP initiation
3. For the first co-primary endpoint only, SE cessation observed without administration of medications for the acute treatment of SE* from the time of IP initiation through 30 minutes following the onset of SE cessation

*Medications for the acute treatment of SE are defined as AEDs administered to abort ongoing SE or prevent imminent recurrence of SE based on clinical or EEG evidence. This definition excludes maintenance doses of AEDs or medications with anticonvulsant properties used for other reasons, such as procedural sedation.

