3.3.1 Adverse Events

Adverse events (AEs) will be coded by MedDRA® version 22.0 or higher and grouped by SOC and PT. The verbatim term will be included in the AE listings. Except where indicated, the summary tables will include only TEAEs. All AEs, treatment-emergent or otherwise, will be presented in participant data listings.

A treatment-emergent adverse event (TEAE) is defined as an AE that occurred or worsened at the time of or following IP initiation. To allow differentiation between the study period in which an AE occurred, two categories are defined based upon onset date. Adverse events that had onset dates prior to the IP initiation are considered "prior." Adverse events with onset dates on or after IP initiation and up to the end of the follow-up period are considered "on-therapy" or equivalently "treatment emergent". Adverse events with onset dates prior to the IP initiation but that worsen after IP starts will be considered treatment emergent.

An overview table, including number and percentage of participants with AEs, TEAEs, TEAEs by highest severity, serious TEAEs, study drug related TEAEs, TEAEs leading to IP discontinuation, and TEAEs leading to death will be provided.

In addition, the following summary tables will be provided:

- TEAE by SOC and PT
- TEAEs by PT
- TEAE by SOC, PT, and severity
- Study drug related TEAE by SOC and PT
- Serious TEAE by SOC and PT
- Serious and drug-related TEAE by SOC and PT
- TEAEs leading to study drug discontinuation by SOC and PT
- TEAEs leading to withdrawal

All AE tables will be sorted by SOC and PT in decreasing frequency of the number of participants in the GNX-treated group. If frequency ties, the sorting will be alphabetic.

A participant having the same AE more than once will be counted only once in the number and percentage of participants' calculation for that AE. Similarly, if a participant had more than one AE in a SOC, the participant will be counted only once in the number of participants with an AE for that SOC. If a participant has the same AE on multiple occasions, the highest severity (severe > moderate > mild) recorded for the event will be presented in the AEs by severity table.

Adverse event listing will be provided for all TEAE, serious TEAEs, TEAE related to IP, TEAE leading to study drug discontinuation, AEs leading to withdrawal, and participants who died during the study.

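### Relapse of SE after full recovery is automatically an SAE while persisting SE by default is not, so response can shift the serious-event comparison in SAP 3.3.1

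*Protocol*

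**What the plan says.** Protocol 8.1.4 handles the disease under study in three ways.

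- Persisting SE: "SE signs and symptoms that were present at study entry and that varied in intensity over the duration of study treatment are not considered AEs". The exception is worsening that the investigator judges to be unexpected.
- Worsening: "significant worsening of the symptoms should be recorded as an AE". Such an event becomes an SAE if it meets a criterion in Protocol 8.2.3, for example "Requires inpatient hospitalization or prolongation of existing hospitalization". Section 8.2.3 makes no exception for SE.
- Relapse after full recovery: "if all seizure activity resolved and the participant returned to baseline status, but SE recurred, the event would then be recorded as an SAE". No separate seriousness test is applied.

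Under Protocol 8.2.4, SAEs "are collected from the time of IP initiation until the final study follow-up visit/contact". Protocol 7.1.3 adds: "The follow-up period for this protocol is approximately 4 weeks".

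SAP 3.3.1 plans a participant overview that includes serious TEAEs, a listing, and a table "Serious TEAE by SOC and PT". SAP 3.3 bases safety summaries on the Safety Population, which is everyone who received IP (SAP 2.2.1). SAP 2.1 takes percentages over the whole treatment group unless stated otherwise. Nothing in SAP 3.3.1 separates recurrence of SE from other serious events or relates it to how many participants had resolved.

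**The concern.** A participant can have the recurrence SAE only after resolving fully. Full resolution is something that treatment is meant to change, so the number who can have this event may differ by arm for reasons unrelated to harm. SE that does not stop is counted mainly as efficacy (cessation, IV anesthesia, SRSE). The same disease activity can therefore land in a safety table or an efficacy table, depending on how the participant responded earlier.

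Safety is part of the primary objective (Protocol 2.2.1), and the Day 2 dosing text in Protocol 6.2.3 expects relapse in some participants. With about 100 randomized, a handful of recurrence events could shape the serious-event picture. As planned, the tables would not show whether an imbalance, or the lack of one, reflects drug harm or who was in a position to relapse.

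**Working it through.** **Inputs.** From the documents: planning response rates of 75% (ganaxolone) and 45% (placebo), with 62 per arm (Protocol 10.2); 100 randomized 1:1, so about 50 per arm (SAP 3.5). Assumed, because the documents give no figures: relapse probability r per fully resolved participant, 10% to 40%; share q of the remaining participants who resolve fully later; share w of never-resolving participants whose SE is reported as an SAE through worsening. The 75% and 45% are used only as a proxy for full resolution.

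**1. The plan's own figure.** The plan states at least 90% power per co-primary endpoint. The normal approximation gives z = (0.30·√62 − 1.96·√(2·0.60·0.40)) / √(0.75·0.25 + 0.45·0.55) = (2.362 − 1.358)/0.660 = 1.52, which is power of 93.6%. Fisher's exact test gives 91.4%. The planning rates are used consistently. The plan states no figure for recurrence SAEs.

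**2. Equal relapse, nobody else resolves.** P(recurrence SAE) = P(full resolution) × r.

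| r | Ganaxolone | Placebo | Expected events, 50 per arm |
|---|---|---|---|
| 10% | 7.5% | 4.5% | 3.8 vs 2.3 |
| 20% | 15.0% | 9.0% | 7.5 vs 4.5 |
| 30% | 22.5% | 13.5% | 11.3 vs 6.8 |
| 40% | 30.0% | 18.0% | 15.0 vs 9.0 |

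The ratio is 0.75/0.45 = 1.67 on every row because r cancels. It depends only on the proxy, so its constancy is not evidence of robustness.

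**3. Late resolution.** SAEs are collected for about 4 weeks, so anyone who resolves later is also at risk. The at-risk shares become 0.75 + 0.25q and 0.45 + 0.55q.

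| q | Ganaxolone at risk | Placebo at risk | Ratio |
|---|---|---|---|
| 0% | 75.0% | 45.0% | 1.67 |
| 25% | 81.2% | 58.8% | 1.38 |
| 50% | 87.5% | 72.5% | 1.21 |
| 75% | 93.8% | 86.3% | 1.09 |
| 100% | 100% | 100% | 1.00 |

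**4. Unequal relapse (q = 0).** The arms tie when the relapse ratio, ganaxolone to placebo, is 0.45/0.75 = 0.60. Below that the direction reverses: with placebo relapse of 30% and a ratio of 0.5, the rates are 0.75 × 0.15 = 11.2% against 0.45 × 0.30 = 13.5%.

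**5. SAEs from SE that never resolves (q = 0).** Totals are 0.75r + 0.25w and 0.45r + 0.55w. They are equal when 0.30r = 0.30w, that is, when w = r. At r = 20%: 15.0% vs 9.0% for w = 0, 20.0% vs 20.0% for w = 20%, and 25.0% vs 31.0% for w = 40%.

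**6. Proxy against trigger.** Protocol Appendix 1 defines cessation for efficacy by a seizure burden below 20% that is also at least 50% lower than before IP. The SAE trigger requires that no seizure activity remains and that the participant is back at baseline. The trigger is stricter, so the true at-risk shares are unknown and need not stand at 75% and 45%.

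**The case against.** A reader might infer that only responders can have an SE-related SAE, so that the more effective arm must show more SAEs. The documents do not support this. Worsening of persisting SE is a second route through 8.1.4 and 8.2.3 (step 5), and late resolvers join the at-risk group (step 3). The rule fixes who can have the event, not how many do. Protocol 10.4.1 aims at durable as well as rapid cessation, so equal relapse per resolved participant cannot be presumed (step 4).

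It can also be said that the preferred-term table and the listing already make SE events visible, and that no safety hypothesis test is planned, so no formal decision is biased. Both points are right, and they limit the importance of the concern. They do not remove it. An SE row may mix relapse with worsening. Because the overview counts participants with any serious TEAE, the SE row cannot be subtracted from it: one participant may have several SAEs.

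Two objections constrain the remedy, and both stand. Making the count without recurrence the main comparison would push possible relapse during or after the taper into the background. A recurrence rate among resolved participants conditions on a post-randomization event, unlike SAP 3.2.4.2, which restricts by ventilation status at baseline. Return to baseline is also not clearly collected: the cessation questionnaire uses the burden definition.

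**Conclusion.** The recording rule is asymmetric, and SAP 3.3.1 has nothing that offsets it. The crude serious-TEAE comparison can therefore be shifted by response rather than by harm. The shift cannot be predicted from the documents. The ratio of 1.67 needs the planning rates to equal full-resolution rates, equal relapse in both arms and no late resolution. Relaxing the last condition brings it down towards 1.00, a relapse ratio below 0.60 reverses it, and SAEs from never-resolving SE can cancel or reverse the total. The supported conclusion is that the comparison may be distorted in either direction and that the planned tables would not show which. No efficacy conclusion is affected. The addition is worth making because it is cheap and makes the serious-event tables readable.

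**What to change.** Leave the 8.1.4 rule and all planned SAE tables as they are. In SAP 3.3.1:

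1. Add a side-by-side participant-level summary of serious TEAEs with and without SE-recurrence SAEs. Identify recurrence by a rule fixed before unblinding that separates it from worsening of persisting SE.
2. In the same table, show by arm the number with an SE-recurrence SAE next to the number whose SE never stopped. Use the full Safety Population as denominator for both, and state the definition of not stopping and its time window.
3. Footnote the serious TEAE tables with the 8.1.4 rule.

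Give a recurrence rate among participants who resolved only if return to baseline can be derived, and label it descriptive because resolution occurs after randomization.

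The cost is one extra table and the classification rule. The recurrence events themselves are already recorded as SAEs.
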